# **Template Instructions**

#### Sections that do not apply:

- In several sections, the addition of checkboxes for **Not Applicable** have been added to the template as responses.
  - If an N/A checkbox is present, select the appropriate justification from the list.
  - If an N/A checkbox is not present, or if none of the existing checkboxes apply to your study, you must write in your own justification.
- In addition:
  - For research where the only study procedures are records/chart review: Sections 19, 20, 22, 23, 24, 25, 31, and 32 do not apply.
  - *For exempt research: Sections 31 and 32 do not apply.*

#### Studies with multiple participant groups:

• If this study involves multiple participant groups (e.g. parents and children), provide information in applicable sections for each participant group. Clearly label responses when they differ. For example:

Response:

Intervention Group: Children with DKA who receive DKA management with intravenous fluids primarily containing lactated ringers

Control Group: Children with DKA who receive DKA management with intravenous fluids primarily containing normal saline

#### Formatting:

• Do not remove template instructions or section headings when they do not apply to your study.

If you are pasting information from other documents using the "Merge Formatting" Paste option will maintain the formatting of the response boxes.

#### Amendments:

- When making modifications or revisions to this and other documents, use the **Track Changes** function in Microsoft Word.
- Update the version date or number on Page 3.

# **PROTOCOL TITLE:**

Include the full protocol title.

Response:

A single-center randomized double blind controlled clinical trial of intravenous fluid content in children with diabetic ketoacidosis admitted to the pediatric intensive care unit

# **VERSION:**

Include the version date or number.

Response:

Protocol version number: 3.0 Version date: May 23, 2019

# **GRANT APPLICABILITY:**

Indicate whether this protocol is funded by a grant (e.g. NIH, foundation grant). For a grant with multiple aims, indicate which aims are covered by this research proposal.

NOTE: This question does not apply to studies funded by a sponsor contract.

Include a copy of the grant proposal with your submission.

Response:

This study is funded by a Wildermuth Foundation

The grant application will be included with this submission.

# **RESEARCH REPOSITORY:**

Indicate where the research files will be kept, including when the study has been closed. The repository should include, at minimum, copies of IRB correspondence (approval, determination letters) as well as signed consent documents. This documentation should be maintained for 3 years after the study has been closed.

Response:

All data files will be entered electronically in the REDCap database. Paper documents will be stored in the Research Document Store Office (room 5154), Conventus Building, [name]

# **1.0 Objectives**

1.1 Describe the purpose, specific aims, or objectives of this research.

Response:

**Aim 1:** To compare the duration of acidosis after admission in children randomized to receive intravenous fluids containing normal saline (NS) to those receiving intravenous fluids containing lactated ringers (LR) during the treatment of diabetic ketoacidosis in the pediatric intensive care unit.

**Aim 2:** To correlate the duration of acidosis with the length of hospitalization and intensive care unit stay after admission in children randomized to receive intravenous fluids containing normal saline to those receiving intravenous fluids containing lactated ringers during the treatment of diabetic ketoacidosis in the pediatric intensive care unit.

1.2 State the hypotheses to be tested, if applicable.

*NOTE:* A hypothesis is a specific, testable prediction about what you expect to happen in your study that corresponds with your above listed objectives.

Response:

**Primary hypothesis:** Children with diabetic ketoacidosis (DKA) who are treated with intravenous fluids containing lactated ringers will have a shorter duration of metabolic acidosis after hospital admission than those treated with intravenous fluids containing normal saline.

**Secondary hypothesis:** The duration of acidosis after hospital admission in children with DKA will be positively associated with length of stay in the intensive care unit and hospital.

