# 2.0 Scientific Endpoints

2.1 Describe the scientific endpoint(s), the main result or occurrence under study.

*NOTE:* Scientific endpoints are outcomes defined before the study begins to determine whether the objectives of the study have been met and to draw conclusions from the data. Include primary and secondary endpoints. Some example endpoints are: reduction of

symptoms, improvement in quality of life, or survival. Your response should **not** be a date.

Response:

The **primary** study outcome will be the duration of metabolic acidosis after hospital admission.

Resolution of metabolic acidosis will be defined in three ways to delineate the iatrogenic effect from intravenous fluids from that of the primary pathology in diabetic ketoacidosis:

- 1. Serum ketone level <1mmol/L;
- 2. Venous pH > 7.3;
- 3. Serum bicarbonate level > 15mmol/L.

**Secondary outcomes**: Length of stay in the pediatric intensive care unit and length of stay in the hospital.

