DKA, the anion gap and ketosis have resolved, but acidosis persists due to an abnormally high chloride level caused by large volumes of NS coupled with the increased absorption of chloride by the kidney as less bicarbonate is generated due to the excretion of ketones in urine [8-10]. In retrospective data, the occurrence of HMA in DKA was correlated with a delayed resolution of acidosis and prolonged hospital stay. A prolonged hospital stay is associated with preventable financial burden, overutilization of health care resources, and missed days of work and school.

Lactated Ringers is an intravenous fluid that not only has lower chloride content than NS but also buffers acidosis by generating bicarbonate from lactate. By mitigating the rates of or severity of HMA, use of LR could potentially shorten length of stay and the morbidity of prolonged hospitalization.

There have been limited prospective clinical studies in pediatric patients examining the association of the chloride content of intravenous fluids and outcome in DKA. This prospective randomized controlled trial is being performed to compare the duration of acidosis and hospital length of stay in children with DKA who are admitted to a pediatric intensive care unit and are treated with intravenous fluids containing NS or LR. The primary study hypothesis is that use of LR will be associated with decreased duration of hyperchloremic metabolic acidosis and, therefore, shorter hospitalization than use of NS in the treatment of pediatric DKA.

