After admission to the PICU, DKA fluid management uses a two-bag system to maintain glucose levels between 100 and 300 mg/dL. Once the patient's glucose concentration falls below 300 mg/dL, the intravenous fluids containing dextrose are started and the fluids without dextrose are titrated downward. In addition to containing necessary electrolytes, the study intravenous fluids will contain either lactated ringer's or normal saline based on the assigned treatment arm.

Study fluid management of the two-bag system will follow the same guidelines for rate of fluid delivery and amount of dextrose used currently in the routine management of patients in DKA. Bedside healthcare personnel will treat all study subjects identically regardless of treatment arm. To provide blinding to all bedside staff, intravenous fluid bags will be labelled as "DKA study fluid with dextrose" or "DKA study fluid without dextrose." The fluid bags will be covered with an opaque black bag to mask any visible description of the fluid content.

Fluids will be adjusted using the study protocol as outlined here:

Serum Glucose	DKA study fluids without dextrose	DKA study fluids with dextrose	
>300mg/dL	100% of the hourly rate	0%	

200-300 mg/dL	50% of the hourly rate	50% of the hourly rate	
<200 mg/dL	0%	100% of the hourly rate	

Study participants will not receive any additional laboratory tests other than those that are already involved in standard DKA management. Currently, routine DKA management involves hourly finger-stick or laboratory glucose levels, every 2-hour serum electrolytes and blood gases, every 6-hour serum beta-hydroxybutyrate levels, and urine ketones with every void. This will be the same for all study participants on both treatment arms.

The study fluids will be used until the acute management of DKA using the continuous insulin infusion and two-bag fluid system is stopped. This will occur when the venous pH is equal to or greater than 7.30, the serum bicarbonate level is equal to or greater than 15 mmol/L and serum ketone levels are less than 1mmol/L.

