#### Response:

Study participation begins from randomization to hospital discharge. The study intervention will cease once acute DKA management is stopped in the PICU prior to floor transfer. The choice of intravenous fluid, if any needed, will then be left to the discretion of the managing team.

11.3 Describe the estimated duration for the investigators to complete this study (i.e. all data is collected and all analyses have been completed).

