#### Response:

Univariate analysis will be used to determine if the subjects in each treatment arm differ at baseline through t-test or Wilcoxon Rank Sum testing for continuous data and Chi-square testing for categorical data. Any differences will be controlled for in the analysis of the primary outcome (length of acidosis) using linear regression. All outcomes will be correlated with the overall chloride load given via intravenous fluids during DKA management. All analyses will be performed using IBM SPSS software, version 25 (Chicago, IL) and SAS (SAS Institute Inc., Cary, NC) with significance set at p<0.05.

17.2 If applicable, provide a power analysis.

*NOTE:* This may not apply to certain types of studies, including chart/records reviews, survey studies, or observational studies. This question is asked to elicit

whether the investigator has an adequate sample size to achieve the study objectives and justify a conclusion.

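### Aim 2 correlates acidosis duration with a stay that already contains much of it, and the analysis plan names no comparison of stay between the NS and LR arms

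*Combined protocol and SAP*

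**What the plan says.** Aim 2 (section 1.1) is "To correlate the duration of acidosis with the length of hospitalization and intensive care unit stay after admission" in the randomized children. The secondary hypothesis (section 1.2) is that "The duration of acidosis after hospital admission in children with DKA will be positively associated with length of stay in the intensive care unit and" (the sentence then adds the hospital). It names no fluid.

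Section 2.1 gives the secondary outcomes as "Length of stay in the pediatric intensive care unit and length of stay in the hospital". Section 3.1 says the trial is being done to compare acidosis duration and hospital stay under the two fluids, and expects that "use of LR will be associated with decreased duration of hyperchloremic metabolic acidosis and, therefore, shorter hospitalization than use of NS".

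Two passages link resolution to leaving the PICU. Section 10.1: "The study fluids will be used until the acute management of DKA using the continuous insulin infusion and two-bag fluid system is stopped". The stopping rule follows: "This will occur when the venous pH is equal to or greater than 7.30", together with bicarbonate and ketone thresholds that nearly match the resolution criteria in section 2.1. Section 11.2: "The study intervention will cease once acute DKA management is stopped in the PICU prior to floor transfer".

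The analysis plan (section 17.1) has three parts: baseline tests by arm; a model for the primary outcome ("Any differences will be controlled for in the analysis of the primary outcome (length of acidosis) using linear regression"); and a correlation of every outcome with the chloride load from intravenous fluids. Only the last reaches length of stay.

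**The concern.** There are two linked problems.

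First, the association test sets a part against a whole. If stay is acidosis time plus whatever follows, the two correlate positively even when what follows has nothing to do with acidosis duration. The secondary hypothesis can then be confirmed without showing that faster resolution changes anything afterwards, or that the fluids differ.

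Second, the question set out in section 3.1, whether children given LR leave hospital sooner than children given NS, has no named test, model or estimate. Randomization gives an unbiased answer to it. The chloride-load correlation does not, because total load depends on how long the fluids run. It is therefore tied to stay in its own right and is not a randomized comparison.

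At stake is the reading of the secondary results. A positive correlation could be reported as the Aim 2 finding while the between-arm result on both secondary outcomes is left to choices made after the data are seen.

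**Working it through.** **Overlap, from the text.** For a child who stays on protocol, acute management ends at resolution (10.1), in the PICU and before floor transfer (11.2). Duration is counted from hospital admission (1.2, 2.1). Hospital stay L is therefore D + R, where D is acidosis duration and R the time from resolution to discharge. PICU stay contains only the part of D after PICU arrival.

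**The plan's own figures.** It gives none for length of stay or for the correlation, so there is none to reproduce. The only spread is in section 17.2, where the quartiles are printed ambiguously (IQR 1-3, 4-8 and IQR 1-3, 3-14). I read them, as an assumption, as 4 to 8 h for anion gap closure and 3 to 14 h for the further time to resolution. The SD of D then depends on how the phases combine:

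- Quartiles added (7 to 22 h): 15/1.349 = 11.1 h. This supposes that the phases move together.
- Phases independent: √(2.97² + 8.15²) = 8.7 h.
- A lower value of 6 h is included as a further assumption.

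**Built-in correlation.** With R independent of D, r = SD_D / √(SD_D² + SD_R²). For n = 104 at two-sided 0.05 (the level in 17.1; sidedness assumed), the chance of a significant positive result is Φ(atanh(r)·√101 − 1.96). Example with SD_D = 11.1 and SD_R = 48: r = 11.1/49.3 = 0.23, and the chance is about 64%.

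| SD of remainder (assumed) | SD_D 6 h | SD_D 8.7 h | SD_D 11.1 h |
|---|---|---|---|
| 6 h | r 0.71, about 100% | r 0.82, about 100% | r 0.88, about 100% |
| 12 h | r 0.45, 99.8% | r 0.59, about 100% | r 0.68, about 100% |
| 24 h | r 0.24, 70% | r 0.34, 95% | r 0.42, 99% |
| 48 h | r 0.12, 24% | r 0.18, 44% | r 0.23, 64% |

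With no part-whole link, the chance of a significant positive result would be 2.5%. It stays at or above 80% until the remainder SD is about 3.5 times the duration SD.

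**Simulation check.** In 10,000 trials with no arm effect and R independent of D (SD_D 11.9 h, SD_R 12 h), the correlation of D with L was significant in 100%. A rank comparison of L between arms rejected in 4.8%, close to its nominal 5%.

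**What a between-arm comparison could detect.** With 52 per arm at two-sided 0.05, the difference detectable with 80% power is (1.960 + 0.842)·SD·√(2/52):

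| SD of stay (assumed) | Detectable difference | Power for 8 h |
|---|---|---|
| 12 h | 6.6 h | 92% |
| 24 h | 13.2 h | 40% |
| 36 h | 19.8 h | 20% |
| 48 h | 26.4 h | 13% |

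**The case against.** The strongest reply is that the comparison is already intended. Section 3.1 says the trial is performed to compare hospital stay between the fluids, section 2.1 lists both stays as secondary outcomes, and Aim 2, though garbled, mentions both randomized groups. That stands as far as intention goes. What is missing is the method: Aim 2 asks for a correlation, and section 17.1 gives no test or estimate for stay by arm. Nor does any passage say whether the correlation would pool the arms.

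A reader might infer that PICU stay equals acidosis time plus a remainder. The documents do not support that. Duration starts at hospital admission, and about 90% of subjects come through the ED (5.2), so some acidosis may precede PICU arrival. Resolution is defined three ways (2.1), whereas fluids stop only when all criteria are met (10.1). Children withdrawn to open-label fluids (20.1) need not follow the stopping rule, and PICU laboratory collection ends near 36 h after the first ED labs for children still in DKA (10.2). The two overlap; they are not identical.

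It is also fair to say that the size rests on assumed SDs and ambiguous quartiles, and that a remainder negatively related to duration would weaken the built-in correlation. How far acidosis duration tracks stay is, besides, a legitimate descriptive question, and the hypothesis as worded makes no claim for LR.

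Finally, replacing total stay by time after resolution would not test the idea in section 3.1. If LR shortens stay by exactly the acidosis time saved, that association would be null although the idea is true.

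**Conclusion.** The point holds in a limited form. For children on protocol, acidosis duration and stay overlap by design, so the Aim 2 correlation leans positive whatever the fluids do. The effect is likely strong for PICU stay, where little time may follow resolution, and may be modest for hospital stay. The figures assume a remainder independent of duration and SDs that the documents do not state.

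A reader might go further and call the secondary hypothesis true by construction. That is not shown: with a remainder SD of 48 h, the chance of significance is only about 24% to 64%.

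The absence of a between-arm analysis of stay from section 17.1 is a matter of text and depends on none of these assumptions. It concerns secondary outcomes only, and the primary comparison is unaffected. It should be corrected before analysis.

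**What to change.** In sections 1.1 and 17.1, make the analysis of the secondary outcomes a comparison of PICU and hospital length of stay between the randomized NS and LR arms, with an estimate and confidence interval. A Wilcoxon rank sum test with a matching estimate of shift would suit, since stay is likely to be skewed. Bring the hypothesis in 1.2 into line.

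Keep the correlation of duration with total stay as descriptive only. State that stay contains the duration and that the correlation is not evidence that LR shortens stay.

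An analysis of duration against time after resolution is optional and exploratory. It would need one stated definition of resolution and discharge clock times; section 18.1 A lists discharge dates, so new data fields may be required.

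The cost is protocol wording and a small amount of analysis, since length of stay is already collected (10.2). There are two downsides. The between-arm comparison may have modest power (40% for an 8 h difference if the SD of stay is 24 h), and the correlation would no longer count as confirming the secondary hypothesis.

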# 2.0 Scientific Endpoints

2.1 Describe the scientific endpoint(s), the main result or occurrence under study.

*NOTE:* Scientific endpoints are outcomes defined before the study begins to determine whether the objectives of the study have been met and to draw conclusions from the data. Include primary and secondary endpoints. Some example endpoints are: reduction of

symptoms, improvement in quality of life, or survival. Your response should **not** be a date.

Response:

The **primary** study outcome will be the duration of metabolic acidosis after hospital admission.

Resolution of metabolic acidosis will be defined in three ways to delineate the iatrogenic effect from intravenous fluids from that of the primary pathology in diabetic ketoacidosis:

- 1. Serum ketone level <1mmol/L;
- 2. Venous pH > 7.3;
- 3. Serum bicarbonate level > 15mmol/L.

**Secondary outcomes**: Length of stay in the pediatric intensive care unit and length of stay in the hospital.

# 3.0 Background

3.1 Provide the scientific or scholarly background, rationale, and significance of the research based on the existing literature and how it will contribute to existing knowledge. Describe any gaps in current knowledge. Include relevant preliminary findings or prior research by the investigator.

Response:

Diabetic Ketoacidosis occurs in approximately 30% of children with new onset type 1 diabetes mellitus (T1DM) and 5-10% of newly diagnosed children with type 2 diabetes [1]. DKA is a decompensated metabolic state resulting from insulin deficiency. DKA is characterized by acidosis, ketonemia, ketonuria, and hyperglycemia. Mortality from DKA in the United States is about 0.15%. Morbidity related to DKA is caused by shock, intestinal ischemia, cardiac arrhythmias, thrombosis, and cerebral edema [2, 3]. Clinically significant cerebral edema occurs in just 0.3-1% of all DKA, but results in 55-87% of all deaths related to DKA. The exact etiology of cerebral edema in DKA remains unclear, but it is consistently associated with osmotic shifts, hypoventilation, cerebral hypoperfusion, and administration of bicarbonate. With the intent to prevent shock, ischemia, and the thrombotic state, providers tend to administer large amounts of intravenous fluids in the form of 0.9% saline, also called normal saline, to patients in the initial treatment of DKA. Aggressive fluid administration has been shown to increase the risk of cerebral edema and does not reverse the primary metabolic deficiency driving the acidosis [4, 5].

During the treatment and recovery phases of DKA, the continued use of aggressive amounts of NS may be the mechanism by which patients develop a hyperchloremic metabolic acidosis (HMA) as NS contains a higher chloride concentration than serum. The detrimental clinical consequences of a high chloride load from intravenous fluids have been demonstrated in patients after trauma, in acute kidney injury, and in certain shock states [6, 7]. During HMA in

DKA, the anion gap and ketosis have resolved, but acidosis persists due to an abnormally high chloride level caused by large volumes of NS coupled with the increased absorption of chloride by the kidney as less bicarbonate is generated due to the excretion of ketones in urine [8-10]. In retrospective data, the occurrence of HMA in DKA was correlated with a delayed resolution of acidosis and prolonged hospital stay. A prolonged hospital stay is associated with preventable financial burden, overutilization of health care resources, and missed days of work and school.

Lactated Ringers is an intravenous fluid that not only has lower chloride content than NS but also buffers acidosis by generating bicarbonate from lactate. By mitigating the rates of or severity of HMA, use of LR could potentially shorten length of stay and the morbidity of prolonged hospitalization.

There have been limited prospective clinical studies in pediatric patients examining the association of the chloride content of intravenous fluids and outcome in DKA. This prospective randomized controlled trial is being performed to compare the duration of acidosis and hospital length of stay in children with DKA who are admitted to a pediatric intensive care unit and are treated with intravenous fluids containing NS or LR. The primary study hypothesis is that use of LR will be associated with decreased duration of hyperchloremic metabolic acidosis and, therefore, shorter hospitalization than use of NS in the treatment of pediatric DKA.

